Limited real-world data are available on the antibody response after COVID-19 vaccination comparing HIV-negative and HIV-positive individuals. There are also limited information that would allow the potential usage of quantitative antibody testing to determine those at greatest risk for infection while could help in guiding the timing of additional vaccinations. There are also limited information on the antibody response of vaccine boosting in individuals, especially those with altered immune response that might lead to no response or low response to the primary vaccination series. At the moment, clinicians must rely on clinical judgement when advising their patients on the utility of vaccine boosting, as well as their level of protection from COVID vaccination. Additional information would be helpful in informing decisions on third doses in different populations such as HIV positive people, whose responses to COVID-19 vaccine and immune status would help define the timing and need for an additional vaccination based on current recommendations. Real-world evidence is needed to better inform such decisions.

3. Research Objectives

PRIMARY OBJECTIVE(S)

Objective #1: Describe COVID-19 vaccine response including frequency of non-response, low response, and adequate response as measured by antibody test by HIV status (e.g., rates, and relationship to demographic and clinical characteristics, as well as vaccine types)

Objective #2: Describe rate of decline in antibody levels over time by HIV status, vaccine type, and baseline CD4 count after initial vaccination as well as other parameters.

SECONDARY OBJECTIVE(S)

Objective #3: Describe response to COVID-19 boosters given (vaccine types, concordant vs. discordant boosters, duration from initial vaccine completion, antibody response, and side effects)

Objective #4: Describe rate of decline in antibody levels over time by HIV status, baseline CD4 count, by vaccine given, and after booster vaccination

Objective #5: Recording breakthrough infections after vaccinations and assessing antibody levels pre-breakthrough infection

4. Data Source

AHF MIDTOWN MANHATTAN HEALTHCARE CENTER

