Records will be examined retrospectively to determine which patients, both HIV-positive and negative, were non-responders, or who developed low or adequate quantitative Ig spike antibodies using the Roche Elecsys semi-quantitative spike Ab Ig assay during usual clinical care.

Demographic and clinical characteristics will be summarized by vaccine response level using medians with interquartile ranges (IQR) for continuous variables and frequencies with proportions for categorical variables. Statistical comparisons between vaccine response level will be performed using Pearson's chi-square or Fisher exact tests for categorical variables and Wilcoxon rank-sum test for continuous variables, using an adequate response as the comparator.

Incidence rates and 95% confidence intervals of COVID vaccine adequate response, non-response and low response to COVID vaccines will be estimated using univariate Poisson regression. Incidence rates will be obtained both overall and by vaccine type. The incidence rate is defined as the number of events during follow-up divided by person-time at risk of the event. Estimating incidence rates with Poisson regression allows the use of all person-time time at risk of the outcome, even with differential lengths of follow-up between groups.

Objective #2: Rate of decline in antibody levels over time by HIV status, vaccine type, and baseline CD4 count after initial vaccination

Rates and 95% confidence intervals of antibody levels decay will be estimated among individuals with at least two antibody measurements. Univariate linear regression, will be employed, using the continuous antibody level as the dependent variable, and timing of tests as

the dependent variable. Robust variance estimator will be used to account for repeated measures. Rates of decay will be produced overall, and stratified by HIV status, vaccine type and baseline CD4 cell count.

ANALYSIS OF SECONDARY OBJECTIVES

Objective #3: COVID-19 boosters given

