In the sub-population of Individuals who received a COVID vaccine booster, the following characteristics will be described using medians with interquartile ranges (IQR) for continuous variables and frequencies with proportions for categorical variables: initial and booster vaccine types, concordant vs. discordant boosters, duration between initial vaccine completion and booster dose, antibody response after the booster, and side effects recorded. Post vaccination responses will be determined no earlier than 2 weeks post vaccination.

Objective #4: Rate of decline in antibody levels over time by HIV status, booster type, and baseline CD4 count after booster vaccination

Rates and 95% confidence intervals for changes in antibody levels will be estimated using linear regression, among individuals with at least two antibody measurements, including one after the booster dose. Univariate linear regression, will be employed, using the continuous antibody level as the dependent variable, and timing of tests as the dependent variable. Robust variance estimator will be used to account for repeated measures. Rates of decay will be produced overall, and stratified by HIV status, booster type and baseline CD4 cell count.

Objective #5: Recording breakthrough infections after vaccinations and assessing antibody levels pre-breakthrough infection

Among all individuals with full vaccination and antibody testing, the EHR will be searched for documentation of COVID infection after vaccinations. If breakthrough infections are observed, antibody levels prior to infection will be described. Note: COVID infections may not be recorded in the EHR if diagnosed outside of the clinic.

SENSITIVITY ANALYSES

NA

SUBGROUP ANALYSES

Patients provided COVID boosters will be evaluated by the types and combinations of vaccines they received. Further, patients given sequential antibody tests will be evaluated by vaccine type for response over time.

8. Study Conduct

REGULATORY AND ETHICAL CONSIDERATIONS

OPERA® complies with all HIPAA and HITECH requirements and has received annual institutional review board (IRB) approval by Advarra IRB, including a waiver of informed consent and authorization for use of protected health information

INFORMED CONSENT

Informed consent has been waived for this non-interventional, observational research and authorization for use of the protected health information has been approved by Advarra IRB.

DATA PRIVACY & PERSONALLY IDENTIFIABLE INFORMATION (PII)

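### The decay analyses for Objectives 2 and 4 give a slope for each stratum but no estimate of the difference between strata

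*Combined protocol and SAP*

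**What the plan says.** Objective 2 is a primary objective: "Describe rate of decline in antibody levels over time by HIV status, vaccine type, and baseline CD4 count after initial vaccination". Its analysis, in section 7 (Analysis of Primary Objectives), begins: "Rates and 95% confidence intervals of antibody levels decay will be estimated among individuals with at least two antibody measurements". The model has antibody level as outcome and test timing as its only regressor: "Univariate linear regression, will be employed, using the continuous antibody level as the dependent variable, and timing of tests as" (the sentence goes on to call timing a dependent variable as well, evidently a slip). On variance: "Robust variance estimator will be used to account for repeated measures". The output is: "Rates of decay will be produced overall, and stratified by HIV status, vaccine type and baseline CD4 cell count".

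Objective 4 (section 7, Analysis of Secondary Objectives) repeats this for boosted patients: "Rates and 95% confidence intervals for changes in antibody levels will be estimated using linear regression", among patients with two or more measurements of which at least one follows the booster. Its output is: "Rates of decay will be produced overall, and stratified by HIV status, booster type and baseline CD4 cell count".

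The formal tests in section 7 belong to Objective 1 and compare patient characteristics between response levels. Sensitivity analyses are marked as not applicable. The Subgroup Analyses paragraph says only that patients with sequential tests will be evaluated by vaccine type.

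**The concern.** A univariate regression on time, fitted stratum by stratum, contains no term for how strata differ. The study nevertheless has comparative interests. Its title asks whether titers should guide boosting whatever the patient's HIV status, immunosuppression or age. The Rationale opens with "Limited real-world data are available on the antibody response after COVID-19 vaccination comparing HIV-negative and HIV-positive individuals". Section 6 names HIV-positive versus HIV-negative patients as a subgroup of interest.

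A report built to this plan would put slopes and intervals next to each other, and readers would naturally compare them. Two informal habits mislead. Reading overlapping intervals as no difference is too strict, so a real difference in persistence can be missed. Reading a decline that is significant in one stratum but not in another as a difference is too loose.

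CD4 adds a further problem. It is a continuous measurement, but it is to be handled by strata whose cut-points appear nowhere in the document, and the stratification is not limited to HIV-positive patients.

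**Working it through.** The plan states no sample size, power, significance level or expected slope for decay, so there is no planned figure to reproduce. What follows sizes the consequence in general terms, by a normal approximation with independent strata. Independence is reasonable because the strata within one factor contain different patients. The ratio of standard errors (SEs) between strata is an assumption and is varied.

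**Overlap rule.** Two 95% CIs fail to overlap when |d| > 1.96 × (SE1 + SE2). A direct test of the difference needs only |d| > 1.96 × √(SE1² + SE2²). On the scale of the SE of the difference, the overlap rule therefore has critical value

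c = 1.96 × (SE1 + SE2) / √(SE1² + SE2²).

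With equal SEs, c = 1.96 × 2/√2 = 2.77, and the two-sided error is 2 × (1 − Φ(2.772)) = 0.0056.

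A true difference that gives a direct test 80% power is 1.96 + 0.84 = 2.80 SEs of the difference. Under the overlap rule the power is Φ(2.802 − 2.772) = Φ(0.030) = 0.51.

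| SE ratio | c | Two-sided error | Power where direct test has 80% | Power where direct test has 90% |
|---|---|---|---|---|
| 1 | 2.77 | 0.56% | 51% | 68% |
| 1.5 | 2.72 | 0.66% | 53% | 70% |
| 2 | 2.63 | 0.86% | 57% | 73% |
| 3 | 2.48 | 1.32% | 63% | 78% |
| 5 | 2.31 | 2.11% | 69% | 83% |

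The clinic has 993 HIV-positive and 946 HIV-negative patients in care (section 4). If repeat testing were proportional to these counts and the spread similar, the SE ratio for the HIV contrast would be about √(993/946) = 1.02, close to the first row. Vaccine and CD4 strata could be much less balanced.

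**Hypothetical example.** Take slopes of −10 and −4, each with SE 2. The intervals are −13.9 to −6.1 and −7.9 to −0.1, which overlap. The difference is −6.0 with SE 2√2 = 2.83, giving a 95% CI of −11.5 to −0.5 and p = 0.034.

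**Significant in one stratum only.** If two strata share the same true slope and each has power p against zero, exactly one is significant with probability 2p(1 − p). This is 50% at p = 0.5 (its maximum), 32% at p = 0.8 and 18% at p = 0.9.

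**CD4 categories.** If CD4 were normally distributed with a linear effect, a cut leaving a fraction q below it would retain φ(z_q)²/[q(1 − q)] of the information. A median split retains 2/π = 64%; a cut isolating the lowest 10% retains 0.1755²/0.09 = 34%. The document gives no CD4 distribution, so these figures only illustrate the loss.

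**Does the contrast need new data?** No. In one simulated data set (150 patients per stratum, three tests each, assumed values), the time-by-group coefficient from a joint model with variance clustered by patient was −0.0750 with SE 0.0397. The difference between the two separately fitted slopes and √(SE1² + SE2²) gave the same values.

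**The case against.** The strongest reply is that both objectives set out to describe, and that no hypothesis or significance level is stated for decay. Stratum slopes with CIs deliver what is promised. The comparative sentence in the Rationale concerns antibody response by HIV status; it does not mention decay, vaccine pairs or CD4. This stands to the extent that the planned estimates are not wrong. It does not remove the gap, because a descriptive study can report a difference with its interval, and group differences are part of the question posed in the title.

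A reader might infer that the study's comparisons will be made by checking whether intervals overlap. The documents do not support that: they set no overlap rule and no significance rule for slopes. A careful reader could recover each SE as the CI width divided by 3.92 and compute an unadjusted difference by hand. That route gives no adjusted difference and no continuous CD4 effect.

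A reader might also infer that CD4 cut-points will be chosen after the data are seen. Only their absence from this document is established. Section 9 says the analysis specifications define key study variables, so they may be fixed there.

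Two further objections stand and limit what a contrast can show. The groups are not comparable: median age is 53 years in HIV-positive and 44 in HIV-negative patients (section 4), so an unadjusted slope difference cannot be attributed to HIV. And the contrasts number about five per objective (one for HIV, three vaccine or booster pairs, one for CD4). Three pairs at 5% each already give 1 − 0.95³ = 14% if treated as independent.

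Finally, an Objective 4 slope may run from a pre-booster to a post-booster measurement, in which case it is not decay. Contrasting such slopes would not repair that.

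**Conclusion.** The point holds in a limited form. Objectives 2 and 4 lack any estimate of how decay differs between HIV, vaccine or booster, and CD4 strata, although the study is motivated partly by such differences. The planned stratum slopes remain valid as description.

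The main risk is that overlapping intervals are read as no difference. Under the overlap rule the error rate is about 0.6% rather than 5%, and power is about 51% where a direct contrast has 80%, both at equal SEs. At an SE ratio of 5 the figures ease to 2.1% and 69%. They are generic: the number of patients with two or more tests is not given, so the study's actual power cannot be calculated. Nor do the documents support a claim that the analysis, with or without a contrast, would establish whether HIV status, vaccine or CD4 itself changes persistence.

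**What to change.** Keep the stratum slopes as description and add the following to section 7.

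- For each factor, fit one model with time, group and time-by-group terms, with robust variance clustered by patient. Report the slope difference with 95% CI for HIV-positive versus HIV-negative patients and for vaccine types (Objective 2) or booster types (Objective 4), naming the reference type.
- Within HIV-positive patients, report a time-by-CD4 term with CD4 continuous, and check its form with a spline. If CD4 strata are kept for display, state the cut-points.
- For Objective 4, restrict the contrasts to slopes estimated from post-booster measurements.
- Show each contrast unadjusted and adjusted for covariates already listed in section 6, such as age. To adjust a slope, the covariate must also enter as a covariate-by-time term.
- Label the contrasts exploratory and not controlled for multiplicity.

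No new data are needed. The cost is SAP wording and a few terms: two beyond time for a two-group factor, four for three vaccines, plus those for adjustment and the spline. It also brings about ten additional contrasts across the two objectives and an assumed functional form for CD4. The post-booster restriction will leave fewer patients for Objective 4, by a number the documents do not give.

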The study population will include adults who were fully vaccinated against SARS-CoV-2 virus (i.e., two doses of Pfizer or Moderna vaccines or one dose of the J&J vaccine), and have received a Roche SARS-CoV-2 Semi-Quant Spike Ig Ab test at least 3 weeks after full vaccination as part of their usual clinical care at AHF Midtown Manhattan Healthcare Center.

Incidence rates of COVID vaccine response levels (i.e., adequate, low, non-response) will be estimated using univariate Poisson regression, overall and by vaccine type. Among individuals with at least two antibody measurements, rates of antibody levels decay will be estimated using univariate linear regression, overall and stratified by HIV status, vaccine type and baseline CD4 cell count. In the sub-population of individuals who received a COVID vaccine booster, vaccination and antibody response will be characterized at least 3 weeks after the booster is received. Univariate linear regression will be used to estimate rates of antibody levels decay, among individuals with at least two antibody measurements, including one after the booster dose. Rates of response decay will be produced overall, and stratified by HIV status, booster type and baseline CD4 cell count.

2. Introduction

BACKGROUND

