The design for this study is an observational cohort study utilizing prospectively collected electronic medical record (EMR) data from usual clinical care at AHF Midtown Manhattan Healthcare Center, obtained from the OPERA® Observational Database.

The study population will consist of adults vaccinated against SARS-CoV-2 virus receiving the Roche SARS-CoV-2 Semi-Quant Spike Ig AB test as part of their usual clinical care. These individuals will be followed from vaccination until study end.

EXPOSURES OF INTEREST

Initial vaccination with Pfizer, Moderna, and J&J COVID vaccines, booster vaccination with Pfizer, Moderna, and J&J vaccines, and concordant boosting versus discordant boosting

SUBGROUPS OF INTEREST

HIV-positive versus HIV-negative patients, individuals with at least 2 measurements of antibody levels, and boosted individuals are the subgroups of interest.

STUDY ENDPOINTS

Endpoints for both the primary and secondary objectives are non-responders and low responders and rates of decline of SARS-CoV-2 antibodies

- Non-response will be defined as: 0 to <50 U/mL
- Low response will be defined as: ≥ 51 to ≤ 250 U/mL
- Adequate response will be defined as: >251 U/mL

Roche's Elecsys semi-quantitative spike Ab Ig assay is a commercially available assay that can potentially be utilized to help guide the need for an additional vaccination dose based upon the levels of antibodies that have been previously clinically correlated with neutralizing antibodies. As part of routine care, Ab Ig assays were performed for some patients at the AHF Midtown Manhattan Healthcare Center and results were recorded in their EHR.

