To normalize across different neutralization assays utilized in phase 3 studies of various COVID-19 vaccines, Khoury, et al., estimated that a 50% protective neutralization level equivalent to 20% of the mean titer in the convalescent subjects equates to a measured in vitro neutralization titer of between 1:10 and 1:30 was approximated at 54 international units IU/ml (95% CI 30–96 IU/ml) against wild-type CoV-19 infection.^{xx} During the period of COVID-19 infection where the Delta virus predominated, a quantitative spike Ab's >250 IU/mL was deemed adequate, based on studies that show that an antibody titer of 4-6x wild-type SARS-CoV-2 were required to effectively neutralize Delta viral strains.^{xxi,xxii, xxiii} We thus utilized a threshold level of >250 (5x wild-type ab levels) IU/mL as an adequate vaccine response against circulating Delta virus post last vaccination recommended in a series, a level of <50 IU/mL as a non-responsive post vaccination titer (inadequate for even wild-type Co-V-2 infection), and levels between (50-250 IU/mL) as a low vaccine response. Non and low-responders who had Co-V-2 Spike Ig levels that were inadequate based on the correlation of Spike Ig levels and neutralizing ab correlations relative to the predominant circulating viral strains were offered optional booster vaccinations with subsequent antibody response measurement post vaccination as standard of care. These recommendations are the current one's implemented during the Delta Co-V-2 19 outbreak by the Ministry of Solidarity and Health of France and the COVID Guidelines group in Geneva, where 260 IU/mL and 300 IU/mL, respectively, are considered gray zones of antibody protection against the Delta virus and where booster vaccinations are recommended for consideration.^{xxiv, xxv}

STUDY COVARIATES

Covariates of interest include: age, sex, race, ethnicity, HIV status, region, payer, immunosuppressive conditions, CD4 cell count, comorbid conditions, BMI. This information will be obtained from each patient's electronic health records.

7. Statistical Analysis

ANALYSIS OF DEMOGRAPHICS/BASELINE CHARACTERISTICS

Demographic and clinical characteristics will be summarized in the overall population using medians with interquartile ranges (IQR) for continuous variables and frequencies with proportions for categorical variables.

ANALYSIS OF PRIMARY OBJECTIVES

Objective #1: COVID-19 vaccine non-response and low response as measured by antibody test by HIV status

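### If antibody decline slows over time, the stratum decay slopes in Objectives #2 and #4 depend on which days each stratum was tested, because one straight line is fitted to the untransformed level with no common time window or curvature term.

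*Combined protocol and SAP*

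**What the plan says.** The decay analysis is in section 7, under Objective #2 of the primary objectives. On who enters: "Rates and 95% confidence intervals of antibody levels decay will be estimated among individuals with at least two antibody measurements". On the model: "Univariate linear regression, will be employed, using the continuous antibody level as the dependent variable, and timing of tests as" what must be meant as the predictor (the text calls both variables dependent). On the output: "Rates of decay will be produced overall, and stratified by HIV status, vaccine type and baseline CD4 cell count". A robust variance handles repeated tests within a patient. Objective #4 repeats the model for patients with a test after a booster, with booster type in place of vaccine type. The section on sensitivity analyses is marked not applicable.

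Three statements elsewhere bear on when tests fall.
- Section 6, overview: "These individuals will be followed from vaccination until study end".
- Section 6, endpoints: "As part of routine care, Ab Ig assays were performed for some patients at the AHF Midtown Manhattan Healthcare Center". No test schedule is given.
- Section 6, endpoints, on non-responders and low responders: they "were offered optional booster vaccinations with subsequent antibody response measurement post vaccination as standard of care". Objective #2 gives no rule for ending a patient's series at a booster.

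The documents give no study-end date, vaccination dates, test days by stratum, expected half-life or decay shape.

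**The concern.** A straight line fitted to a curve that flattens gives an average slope that depends on the period covered: early tests alone give a steep slope, and early and late tests together a shallower one. Two strata with the same curve but different test periods would therefore show different rates of decay. The robust variance does not help, because it changes the standard error and leaves the slope as it is.

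The plan leaves room for test periods to differ. Follow-up length depends on the vaccination date, testing is unscheduled, and an accepted booster offer may cut short the primary series in patients with low titres. Decline by HIV status, vaccine type and CD4 count is a primary objective, and HIV-positive versus HIV-negative is a named subgroup contrast. Stratum rates with 95% intervals will be read against each other, so a difference in test timing could be taken for a difference in antibody persistence.

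**Working it through.** The plan states no decay rate, test window or sample size, so there is no figure of its own to reproduce. The check applies the planned model to one known curve over different test periods.

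**Inputs**
- From the documents: raw continuous level regressed on time, one slope per stratum (Objective #2). Day 21 is taken as the earliest test day, from the Synopsis ("at least 3 weeks after full vaccination as part of their usual clinical care") and inclusion criterion 3.
- Assumptions: test days spread evenly over the period; 1000 U/mL at day 0; single-exponential decay with a half-life of 75 days (range 50 to 150); the end days of the test periods.

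**Formula.** For test days uniform on [a, b], with midpoint m = (a+b)/2, the least-squares slope of f(t) on t is 12/(b−a)³ × ∫(t−m) f(t) dt. With f(t) = 1000·e^(−kt) and k = ln 2/75, so 1/k = 108.20 and 1/k² = 11,707.7, the integral is F(b) − F(a), where F(t) = −1000·e^(−kt)·[(t−m)/k + 1/k²].

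**Days 21-120.** m = 70.5 and (b−a)³ = 99³ = 970,299.
- F(120) = −329.877 × 17,063.7 = −5,628,922
- F(21) = −823.591 × 6,351.7 = −5,231,203
- Slope = 12 × (−397,719)/970,299 = −4.919 per day, or −147.6 U/mL per 30 days.

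**Days 21-240.** m = 130.5 and (b−a)³ = 219³ = 10,503,459.
- F(240) = −108.819 × 23,555.8 = −2,563,322
- F(21) = −823.591 × (−140.43) = +115,657
- Slope = 12 × (−2,678,979)/10,503,459 = −3.061 per day, or −91.8 U/mL per 30 days.

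**Effect of the gap between periods (half-life 75 days)**

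| Test period | Slope, U/mL per 30 days | Ratio to days 21-240 |
|---|---|---|
| Days 21-120 | −147.6 | 1.61 |
| Days 21-180 | −115.6 | 1.26 |
| Days 21-210 | −102.8 | 1.12 |
| Days 21-240 | −91.8 | 1.00 |

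For the widest gap the ratio is 1.93, 1.61, 1.45 and 1.29 at half-lives of 50, 75, 100 and 150 days.

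**Does a log scale remove it?**
- Single-exponential decay: log f(t) is a straight line, so every period returns the 75-day half-life and the ratio is 1.00.
- Two-phase decay, assumed as 0.8·2^(−t/40) + 0.2·2^(−t/150): a straight line through the log level has slope −0.01247 per day over days 21-120 and −0.01019 over days 21-240. Half-life = ln 2/|slope| = 55.6 and 68.0 days, a ratio of 1.22. Days 21-180 and 21-210 give 61.3 and 64.6 days, so the ratios of 68.0 to these are 1.11 and 1.05.
- Decline truly linear in U/mL: every period gives the same raw slope, with no distortion.

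**Does a common window on the raw scale suffice?** No. With days 21-120 in every stratum and the same 75-day half-life, starting levels of 500, 1000 and 2000 U/mL give slopes of −74, −148 and −295 U/mL per 30 days. Identical half-lives still look fourfold apart. On the log scale all three agree.

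**The case against.** **The plan does not forecast unequal follow-up.** A reader might infer that it does, because Objective #1 says Poisson regression uses all time at risk "even with differential lengths of follow-up between groups". That is a general property of the method, stated for rates given overall and by vaccine type. It says nothing about test timing by HIV status or CD4 count. The support comes from section 6, and it shows that test periods can differ, not that they do. Longer follow-up need not mean later pre-booster tests. This stands.

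**No slopes are formally compared.** The objective is descriptive, and the plan produces stratified rates without a test or contrast. This stands: the risk lies in how side-by-side rates are read.

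**Curvature and size are assumed.** The documents give no decay shape, and linear decline would leave nothing to correct. This also stands, although the plan neither justifies linearity nor checks it.

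**The 1.6-fold figure mainly measures the missing log transform.** Under its own single-exponential assumption it vanishes on the log scale, and it uses a wide gap between periods. This is right. What belongs to unequal periods alone is the log-scale remainder, about 20% for the widest gap and less for narrower ones, and that needs two-phase decay. Hence scale and time window have to be fixed together.

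**Conclusion.** The point holds conditionally. As written, the stratum slopes in Objectives #2 and #4 are comparable only if decline is linear in U/mL or if all strata were tested over similar periods. The plan secures neither. If decline slows and test periods differ, identical curves would show different rates: 1.12- to 1.6-fold on the raw scale with a 75-day half-life, depending on the gap, and up to about 20% on the log scale under the assumed two-phase mix. These are illustrations, and the real size depends on test timing and decay shape that the documents do not report. A reader might conclude that the plan will report false differences between HIV or CD4 strata; the documents do not support that. Since this concerns a primary objective and costs little to change, the change should be made.

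**What to change.** 1. In Objective #2, regress the log antibody level on time since the last dose.
2. Report stratum slopes in one of two ways: over a single window common to all compared strata, fixed from test dates before titres are examined, with the minimum number of patients tested stated; or from a time spline, evaluated at the same days in each stratum and within the range that all strata cover.
3. Do the same in Objective #4, counting from the booster date.
4. Tabulate test days by stratum. A common window equalises the ends of the period but not the spread of tests inside it, and the table would show any remaining imbalance.

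**Cost.** This needs changed analysis wording, a date filter or spline term, and one table; no new data. With a common window, some late tests are lost, and patients left with fewer than two tests drop out of the stratified estimates, so intervals widen by an amount the documents do not allow one to estimate. The spline avoids most of that loss. The non-response category starts at 0 U/mL, so a log analysis also needs a stated rule for zero or below-limit results. The full-period overall estimate can stay.
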